3.1.1.1 Definition of Clinical Relapse

Clinical relapse is defined as an:

- Increase in partial Mayo Clinic Score (pMCS) ≥ 3 points compared with induction timepoint (Week 10) AND absolute pMCS ≥ 5 AND endoscopic subscore ≥ 2

If a patient meets criteria for clinical relapse during the Maintenance Phase of the study, he or she may withdraw from this study and enroll in Part 1 (OLE) of Study GA28951 to receive open-label etrolizumab treatment, if eligible.

3.1.1.2 Rescue Therapy

Rescue Therapy that Can Be Given with Study Medication for the Treatment of UC

During the Induction Phase (Prior to Week 10):

Patients are required to maintain stable doses of their concomitant medications (oral 5-ASA, corticosteroids, immunosuppressants) for UC.

In the Induction Phase, any patient who requires initiation of an immunosuppressant (AZA, 6-MP, or MTX), corticosteroid, or oral or topical 5-ASA, or who requires an increase in dose over baseline levels for treatment of worsening disease symptoms should stay in the study until Week 10, at which time the patient can enroll in Part 1 (OLE) of Study GA28951 to receive open-label etrolizumab, if eligible, or enter the 12-week safety follow-up in this study and then enroll in Part 2 (SM) of Study GA28951 for extended PML monitoring. These patients will be classified as non-responders at Week 10 and may not continue into the Maintenance Phase of the study.

During the Maintenance Phase:

Initiation or escalation of oral 5-ASA should be avoided but is permitted if deemed clinically necessary by the investigator. Patients who initiate or escalate oral 5-ASA therapy may continue blinded treatment.

Use of topical or IV corticosteroids or topical 5-ASA is not desired as concomitant medication. If these are used to treat clinical symptoms of UC, the patient may remain in the blinded study or may enroll in Part 1 (OLE) of Study GA28951, if eligible, based on the investigator's discretion. Patients who leave the treatment phase early to enroll in Part 1 (OLE) of Study GA28951 should complete the early withdrawal from treatment visit prior to enrollment.

Patients must begin the specified corticosteroid taper at Week 10 during the Maintenance Phase. For patients who cannot tolerate the corticosteroid taper without recurrence of clinical symptoms of UC or symptoms of steroid withdrawal, corticosteroids may be increased (up to the baseline dose, only if required). In such cases, the tapering regimen must be reinitiated within 2 weeks. An increase in corticosteroid dose back to baseline is not considered rescue medication if it occurs during the corticosteroid taper. These patients should remain in the blinded study.

Etrolizumab—F. Hoffmann-La Roche Ltd
37/Protocol GA29102, Version 7

Patients who were not receiving corticosteroids at baseline and patients who have completed the steroid taper who subsequently require oral corticosteroids at a dose greater than 10 mg for 5 days or longer for the treatment of worsening UC symptoms or steroid withdrawal may remain in the blinded study or may enroll in to Part 1 (OLE) of Study GA28951, if eligible, based on the investigator's discretion. Patients who leave the treatment phase early to enroll in Part 1 (OLE) of Study GA28951 should complete the early withdrawal from treatment visit prior to enrollment in Study GA28951.

Endoscopy to document disease activity for patients exiting the treatment period early for any reason is strongly recommended.

Immunosuppressants (AZA, 6-MP, or MTX): Patients are to remain on their stable, baseline dose of immunosuppressant therapy throughout the study unless dose reduction or discontinuation is required due to toxicity. Generally accepted criteria for discontinuation of immunosuppressants due to toxicity include, but are not limited to, acute pancreatitis, severe leukopenia, severe thrombocytopenia, or clinically significant elevations of the liver-associated enzymes from baseline, especially in the presence of an elevated total bilirubin. The ultimate decision to reduce dose or discontinue immunosuppressants due to toxicity remains at the discretion of the investigator. Patients who do initiate or escalate immunosuppressant therapy may remain in the blinded study or may be given the option to enroll in Part 1 (OLE) Study GA28951, if eligible, based on the investigator's discretion. Patients who leave the treatment phase early to enroll in Part 1 (OLE) Study GA28951 should complete the early withdrawal from treatment visit prior to enrollment in Study GA28951.

[figure not shown]
Endoscopy to document disease activity for patients exiting the treatment period early for any reason is strongly recommended.

Rescue Therapy that Cannot Be Given with Study Medication for the Treatment of UC

At ANY time during the conduct of the study, use of other immunosuppressive agents including, but not limited to, anti-integrins, T- or B-cell depleters (except AZA and 6-MP), TNF inhibitors (including TNF inhibitor biosimilars), anti-adhesion molecules, *Janus kinase (JAK) inhibitors*, cyclosporine, tacrolimus, or investigational agents are prohibited. Patients who receive such therapies are not to receive further study treatment or open-label treatment and will be required to enter the 12-week safety follow-up period of this study (see [Appendix 2](#)). These patients will also subsequently be requested to enroll in Part 2 (SM) of Study GA28951 protocol for 92 weeks of extended PML monitoring.

A complete list of study visits and assessments can be found in the Schedule of Assessments (see [Appendix 1](#)).

Figure 1 Study Schema

6-MP = 6-mercaptopurine; AZA = azathioprine; d = day; CS = corticosteroid; MTX = methotrexate; OLE = open-label extension; OLE-SM = open-label extension and safety monitoring; Q4W = every 4 weeks; QOD = every other day; SC = subcutaneous; SM = safety monitoring; TNF = tumor necrosis factor; UC = ulcerative colitis; wk = week.

^a Stable budesonide at ≤ 9 mg/day. Taper from Week 10 to QOD for 2 weeks and then discontinue.

3.1.1.3 Number of Patients

Approximately 350 patients are to be enrolled for this study. Following 10 weeks of open-label induction with etrolizumab, it is estimated that approximately 60% of patients will achieve clinical response, which will provide approximately 105 patients in each treatment arm for the Maintenance Phase. *Additional patients may be enrolled in the Induction Phase if needed to meet sample size requirements for the Maintenance Phase.*

3.1.2 Data Monitoring Committee

An independent Data Monitoring Committee (iDMC) will monitor safety and study conduct on an ongoing basis. Members of the iDMC will be external to the Sponsor and will follow a charter that outlines the iDMC roles and responsibilities. The iDMC will meet approximately every 6 months (frequency adjustable as required) to review unblinded safety and study conduct data prepared by an independent data coordinating center (IDCC). If the iDMC deems a benefit-risk assessment necessary, the iDMC may also review unblinded efficacy data. The iDMC may recommend stopping the study early for safety reasons. However, the iDMC may not recommend stopping the trial early for positive efficacy or solely for futility.

3.2 END OF STUDY AND LENGTH OF STUDY

Length of Study

The total length of the treatment period will be 62 weeks. Patients who do not achieve a clinical response at Week 10, patients who have clinical relapse during the Maintenance Phase, patients who receive defined rescue treatment (see Section 4.3.2.2), and patients who complete 62 weeks of the study may be given the option of enrolling in Part 1 (OLE) of Study GA28951, where they will receive open-label etrolizumab treatment. Those who do not enroll in Part 1 (OLE) of Study GA28951 will continue to 12 weeks of safety follow-up in this study and then be requested to enroll in Part 2 (SM) of Study GA28951 for 92 weeks of PML monitoring.

The total length of the study is expected to last from the first patient screened to either the last patient in last follow-up visit in this protocol or last patient enrolled into Study GA28951 (OLE-SM), whichever is later.

End of Study

The end of the study is defined as the last patient last safety follow-up visit in this protocol or last patient in this protocol enrolled into Study GA28951 (OLE-SM), whichever is later.

3.3 RATIONALE FOR STUDY DESIGN

3.3.1 Rationale for Test Product Dosage

Data from Phase I (Study ABS4262g) and Phase II (Study ABS4986g; EUCALYPTUS) indicated that the 100-mg Q4W regimen is sufficient to maintain β 7 receptor occupancy both in blood and in colonic tissue, is well tolerated, and results in meaningful clinical efficacy, and therefore, will be evaluated further in this Phase III study. The rationale for proposing a 105-mg Q4W SC regimen is discussed below.

- The Phase II 100-mg Q4W SC dose (0.7 mL of 150 mg/mL solution via vial and syringe, with an intended nominal dose of 100 mg) showed clinically meaningful efficacy without clinically meaningful safety imbalances (see Section 1.2). The Phase III formulation is a PFS containing 0.7 mL of 150 mg/mL etrolizumab solution, corresponding to delivering a dose of 105 mg etrolizumab per injection.

In the Phase II EUCALYPTUS study, the 100-mg SC Q4W dose resulted in an increased clinical remission rate in TNF-naive patients (43.8%; $p=0.007$), as well as in the combined TNF-naive and inadequate response to anti-tumor necrosis factor (TNF-IR) group (20.5%; $p=0.004$) at Week 10 as compared with the clinical remission rate in placebo patients (0%). These data suggest that the 100-mg SC Q4W dose regimen is efficacious in patients with moderately and severely active UC.

- Up to a 4–5-fold higher exposure did not result in a greater PD effect or an increase in clinical benefit.

A higher dose (420 mg SC at Week 0 followed by 300 mg at Weeks 2, 4, and 8) was also tested in the EUCALYPTUS study without any major safety concerns. However, there was no clear distinction in observed pharmacological effects (including clinical efficacy outcome and PD response, such as β 7 receptor occupancy) between high-dose and the 100-mg dose cohorts. Although the study was not powered to enable a formal comparison of the two active arms, the data suggest that the observed clinical remission rate at Week 10 in the low-dose cohort was not further improved in the high-dose cohort.

Preliminary concentration quartile-response analysis was conducted, for the data pooled from both low- and high-dose cohorts, to see whether patients in the higher concentration quartiles had better remission rate. The results did not show any exposure response relationship.

- Exposure lower than 100 mg Q4W is likely not sufficient to maintain β 7 integrin receptor occupancy.

In the Phase I study (Study ABS4262g), the etrolizumab PK profile appears nonlinear at a dose level of < 1 mg/kg IV. The duration of β 7 receptor occupancy is dose dependent. A single dose of 0.3 mg/kg IV maintained β 7 receptor occupancy for only approximately 2 weeks, which is likely insufficient to ensure maximal β 7 receptor occupancy at all times within a Q4W dosing interval.

On the basis of data from the Phase II EUCALYPTUS study, it is assumed that maximal/near maximal occupancy of β 7 receptors both in the blood and in colonic tissue is minimally necessary for etrolizumab's clinical activity. Per this assumption, population PK simulations were performed and results showed that a 100-mg SC Q4W regimen can provide steady-state serum trough concentration ($C_{\text{trough,ss}}$) of at least 1.7 $\mu\text{g/mL}$ (the minimum serum concentration observed that maintained colonic tissue β 7 occupancy) in $\geq 84\%$ of patients, whereas a dose lower than the 100-mg SC Q4W regimen (e.g., 50 mg Q4W SC) is likely not sufficient for maintaining β 7 receptor occupancy at all times during the Q4W dosing interval, since only 56% of patients were predicted to reach a 1.7 $\mu\text{g/mL}$ level in their $C_{\text{trough,ss}}$ (see Table 2).

Lower doses are also anticipated to result in etrolizumab serum level falling into the nonlinear PK concentration range and hence are likely to increase variability in exposure.

Table 2 Population Pharmacokinetic Modeling Predicted Percentage of Patients Achieving 1.7- $\mu\text{g/mL}$ Steady-State Trough Concentration under Different Dosing Scenarios

	Q4W SC Dosing		
	300 mg	100 mg	50 mg
Percentage of patients expected to have $C_{\text{trough,ss}} > 1.7 \mu\text{g/mL}$	98	84	56

$C_{\text{trough,ss}}$ = steady-state trough concentrations; PK = pharmacokinetic; Q4W = every 4 weeks; SC = subcutaneous.

Note: 1.7 $\mu\text{g/mL}$ is the minimum serum concentration observed in the Phase II study that maintained β 7 occupancy in the colonic tissue.

In conclusion, on the basis of available etrolizumab efficacy, PK, PD, and safety data (see Section 6.6), a PFS delivering a dose of 105 mg Q4W is considered the most appropriate dosing regimen for this Phase III study.

3.3.2 Rationale for Patient Population

There is a high unmet medical need in moderately to severely active UC due to current treatments being associated with significant adverse events, low rates of sustained remission, or being highly invasive (i.e., colectomy) (see Section 1.1 for details).

The Phase II EUCALYPTUS trial of etrolizumab versus placebo provided evidence of efficacy, including induction of remission at Week 10, in patients with moderately to severely active UC refractory to or intolerant of conventional and/or TNF inhibitor therapies. Results from this trial showed that in the TNF-naïve subgroup, clinical remission (defined as MCS ≤ 2 and all subscores ≤ 1) at Week 10 was observed in 43.8% versus 0% of patients in the 100-mg etrolizumab versus placebo group, suggesting substantial efficacy in the TNF-naïve population at Week 10.

In summary, because of the limitations of the currently available therapies for the treatment of moderately to severely active UC and the favorable benefit-risk observed in the TNF-naïve population in EUCALYPTUS, this Phase III trial is designed to test the efficacy and safety of etrolizumab in this patient population.

[figure not shown]
3.3.3 Rationale for Control Group

A placebo-treated control group will be used in this study in the Maintenance Phase to assess the differences in efficacy, safety, and tolerability in patients who receive etrolizumab plus background UC therapy compared with patients who receive placebo plus background UC therapy. The use of a control group during the maintenance period is necessary given the inherent variability in disease flares and the use of subjective assessments, such as the patient-reported outcomes (PROs). Patients in the control group will undergo the same study assessments as the etrolizumab-treated patients.

3.3.4 Rationale for Biomarker Assessments

A biomarker that may predict an increased chance of response to therapy would be valuable to patients and treating physicians to aid in guiding treatment decisions. Etrolizumab binds to the $\beta 7$ integrin and blocks $\alpha 4\beta 7$:MAdCAM and $\alpha E\beta 7$:E-cadherin binding. In exploratory analyses from the Phase II EUCALYPTUS study, patients with higher baseline biopsy αE gene expression by quantitative polymerase chain reaction (qPCR) and αE^+ cell counts by immunohistochemistry (IHC) had a higher rate of remission at Week 10 (see Figure 2). The baseline levels of αE and other biomarkers will be evaluated in this Phase III study to further assess whether they may function as predictive response biomarkers.

Figure 2 Effects of High and Low Baseline Expression of the α E Biomarker in Colon on the Remission Status of Patients with Ulcerative Colitis Treated with Etrolizumab in EUCALYPTUS (Observed Data)

LD=loading dose; SC=subcutaneous.

All patients enrolled in the current study will have mandatory colonic mucosal sampling at the screening visit to analyze the relationship of α E levels (and potentially other biomarkers) with response to treatment. In addition, samples will be collected at Weeks 10 and 62 for potential exploratory biomarker analyses that include, but are not limited to, α E expression.

3.4 OUTCOME MEASURES

3.4.1 Efficacy Outcome Measures

Primary Outcome Measure

- Remission at Week 62 among *patients with a clinical response at Week 10, as determined by the MCS*

Secondary Outcome Measures

- Clinical remission at Week 62 among patients in clinical remission at Week 10
- Clinical remission at Week 62
- *Remission at Week 62 among patients in remission at Week 10*
- Improvement in endoscopic appearance of the mucosa at Week 62
- Endoscopic remission at Week 62
- Histologic remission at Week 62
- *Change from baseline in rectal bleed subscore at Week 6*
- *Change from baseline in stool frequency subscore at Week 6*
- Corticosteroid-free clinical remission at Week 62 (off corticosteroids for at least 24 weeks prior to Week 62) in patients who are receiving corticosteroids at baseline

- Corticosteroid-free remission at Week 62 (off corticosteroids for at least 24 weeks prior to Week 62) in patients who are receiving corticosteroids at baseline
- Change from baseline to Week 62 in UC bowel movement signs and symptoms as assessed by the UC-PRO/SS measure
- Change from baseline to Week 62 in UC abdominal symptoms as assessed by the UC-PRO/SS measure
- Change from baseline to Week 62 in patients' health-related QOL as assessed by the overall score of the IBDQ

Exploratory Efficacy Outcome Measures

- *Clinical response at Week 62 among patients with a clinical response at Week 10*
- *Remission at Week 62 among patients in clinical remission at Week 10*
- Corticosteroid-free clinical remission at Week 62 (off corticosteroids for at least 12 weeks prior to Week 62) in patients who are receiving corticosteroids at baseline
- *Histologic disease activity change from baseline to Week 10 and Week 62*
- *Improvement in histologic and/or endoscopic disease activity*
- Change in health utilities, as assessed by the EQ-5D, from baseline to Weeks 10 and 62
- Improvement in endoscopic appearance of the mucosa at Week 10
- Endoscopic remission at Week 10
- Frequency and duration of hospitalizations from Week 10 to Week 62
- *Response, remission and corticosteroid-free endpoints as determined by the mMCS*

3.4.2 Safety Outcome Measures

The safety outcome measures for this study are as follows:

- Incidence and severity of adverse events
- Incidence of serious adverse events
- Incidence and severity of infection-related adverse events
- Incidence of serious infection-related adverse events
- Incidence and severity of injection-site reactions
- Incidence of adverse events leading to study drug discontinuation
- Incidence of laboratory abnormalities
- Incidence of malignancies
- Incidence of ATAs to etrolizumab
- Incidence and severity of hypersensitivity reaction events

3.4.3 Pharmacokinetic Outcome Measures

The PK outcome measures for this study are as follows:

- Serum trough concentration at steady state during the dosing period from Week 12 to Week 62
- Serum concentration at primary endpoint time (Week 62)

3.4.4 Exploratory Biomarker Outcome Measures

The exploratory biomarker outcome measures for this study are as follows:

- Remission at Week 10 and maintenance of remission at Week 62 in patients according to baseline levels of colonic tissue biomarkers and/or peripheral blood, including, but not limited to, α E integrin
- Changes in levels of exploratory colonic tissue and/or peripheral blood biomarkers during the Induction and Maintenance Phases
- Changes in stool biomarkers, which may include, but are not limited to, those in the microbiota and bacterial cultures, during the Induction and Maintenance Phases

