- The primary efficacy endpoint has been changed to remission at Week 62 for patients who achieve clinical response (rather than remission) at Week 10. This change has been made to align with clinical practice standards whereby patients who experience a clinical response during treatment induction continue on treatment and are assessed for remission at a later time point (Sections 2.1, 3.4.1, 6.1, and 6.4.1, Figure 1 and Figure 3).
- To assess the onset of action of etrolizumab, a secondary efficacy endpoint of change in Mayo Clinic Score (MCS) rectal bleeding and stool frequency subscores from baseline to Week 6 has been added (Sections 2.1, 3.4.1, and 6.4.2).
- Secondary and exploratory efficacy endpoints have been amended to align with the revision of the primary efficacy endpoint (Sections 2.1, 3.4.1 and 6.4.2).
- Histologic remission, defined as a Nancy histological index of ≤ 1 , has been added as a secondary efficacy outcome measure. The definition is based on consensus guidelines recommending that histologic remission should be defined by the absence of neutrophils in the crypts and lamina propria (Section 2.1, 3.4.1, 6.4.2 Appendix 12 and Table 1).
- Janus kinase inhibitors have been added to the list of rescue therapies prohibited at any time during the study (Sections 3.1.1.2, 4.3.2.2, and 4.4.2).
- Exclusion criteria have been amended to include any treatment with tofacitinib during screening as this drug has been approved for use in the United States and European Union and is no longer an investigational product (Section 4.1.2).
- The exclusion criterion related to eligibility following receipt of investigational treatments has been modified to account for current molecules in development for the treatment of inflammatory bowel disease. The allowable time period after treatment has been reduced to 5 half-lives of the investigational product or 28 days after the last dose, (whichever is greater) prior to Day 1 of the study (Section 4.1.2).

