- To evaluate change in health utilities, as assessed by the EuroQoL Five-Dimension Questionnaire (EQ-5D), from Week 10 to Week 62
- To evaluate improvement in endoscopic appearance of mucosa at Week 10
- To evaluate endoscopic remission at Week 10
- To evaluate the frequency and duration of hospitalizations from Week 10 to Week 62
- *To evaluate response, remission, and corticosteroid-free endpoints, as determined by the mMCS*

The efficacy outcomes definitions are given in [Table 1](#).

Table 1 Efficacy Outcomes Definitions

Outcome Measure	Outcome Measure Definition
Mayo Clinic Score	MCS is a composite of 4 assessments, each rated from 0–3: stool frequency, rectal bleeding, endoscopy, and physician’s global assessment
Partial MCS	pMCS is a composite of 3 assessments of the MCS, each rated from 0–3: stool frequency, rectal bleeding, and physician’s global assessment
Modified MCS	mMCS is a composite of 3 assessments of the MCS, each rated from 0–3: stool frequency, rectal bleeding, and endoscopy
Remission	MCS ≤ 2 with individual subscores ≤ 1 and a rectal bleeding subscore of 0
Maintained remission	Remission achieved at the start of the Maintenance Phase (Week 10) and maintained at the end of the Maintenance Phase (Week 62).
Clinical remission	MCS ≤ 2 with individual subscores ≤ 1
Maintained clinical remission	Clinical remission achieved at the start of the Maintenance Phase (Week 10) and maintained at the end of the Maintenance Phase (Week 62)
Clinical response	MCS with ≥ 3 -point decrease and 30% reduction from baseline as well as ≥ 1 -point decrease in rectal bleeding subscore or an absolute rectal bleeding score of 0 or 1
Corticosteroid-free clinical remission	Clinical remission with no corticosteroid use for 24 weeks prior to Week 62
Corticosteroid-free remission	Remission with no corticosteroid use for 24 weeks prior to Week 62
Improvement in endoscopic appearance of the mucosa	Endoscopic subscore ≤ 1
Endoscopic remission	Endoscopic subscore = 0
Histologic remission	$NHI \leq 1$ ^a

MCS = Mayo Clinic Score; mMCS = modified Mayo Clinic Score; pMCS = partial Mayo Clinic Score; NHI = Nancy histological index.

^a See [Appendix 12](#)

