6.1 DETERMINATION OF SAMPLE SIZE

The study sample size was selected so that sufficient patients are enrolled to evaluate the primary endpoint in the Maintenance Phase. Approximately 350 patients will be enrolled in the open-label Induction Phase.

Under the assumption of *clinical response* at Week 10 of approximately 60% (based on the Phase II Week 10 *response* results for the TNF-naïve subgroup), the planned size of 350 patients in the open-label Induction Phase would provide approximately 210 patients *randomized into the Maintenance Phase*. A sample size of approximately 105 patients per arm is required in the Maintenance Phase to achieve >90% power to detect a 25% absolute difference in remission rates between the etrolizumab and placebo arms, for a χ^2 test at the two-sided 5% significance level, under the assumption of a placebo true remission rate of 30%–45%. If *clinical response* rates at Week 10 are lower than projected, the total enrollment in the open-label induction cohort may be increased to ensure that a *sufficient* number of Week-10 *clinical responders* are randomized into the Maintenance Phase.

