### **2.2.1 Efficacy Outcome Measures**

#### **Primary Outcome Measure**

- Remission at Week 62 among patients with a clinical response at Week 10, as determined by the Mayo Clinic Score (MCS)

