#### **Exploratory Biomarker Outcome Measures**

The exploratory biomarker outcome measures for this study are as follows:

- Remission at Week 10 and maintenance of remission at Week 62 in patients according to baseline levels of colonic tissue biomarkers and/or peripheral blood, including, but not limited to,  $\alpha$ E integrin

- Changes in levels of exploratory colonic tissue and/or peripheral blood biomarkers during the Induction and Maintenance Phases
- Changes in stool biomarkers, which may include, but are not limited to, those in the microbiota and bacterial cultures, during the Induction and Maintenance Phases

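### The listed biomarker outcome uses maintained remission instead of the primary endpoint, so Week 62 results of randomised patients not in remission at Week 10 cannot inform whether alpha-E predicts benefit

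*Protocol*

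**What the plan says.** Protocol 3.4.4 lists, as an exploratory biomarker outcome measure, "Remission at Week 10 and maintenance of remission at Week 62 in patients according to baseline levels of colonic tissue biomarkers" (and/or peripheral blood, including alpha-E integrin). The protocol synopsis has the same item, and SAP Appendix 1 repeats it: "Remission at Week 10 and maintenance of remission at Week 62 in patients according to baseline levels". None of the three places names a denominator.

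Table 1 in Protocol 2.1 defines remission as "MCS ≤ 2 with individual subscores ≤ 1 and a rectal bleeding subscore of 0", and maintained remission as "Remission achieved at the start of the Maintenance Phase (Week 10) and maintained at the end of the Maintenance Phase (Week 62").

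The current primary endpoint (Protocol 3.4.1 and 6.4.1, study SAP 2.2.1) is Week 62 remission in patients who had a clinical response at Week 10, that is, in everyone randomised. The Version 7 rationale gives the change: "The primary efficacy endpoint has been changed to remission at Week 62 for patients who achieve clinical response (rather than remission) at Week 10".

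Protocol 3.3.4 gives the purpose of measuring alpha-E and other baseline markers: "to further assess whether they may function as predictive response biomarkers". It makes the screening biopsy mandatory for all enrolled patients.

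**The concern.** A predictive marker is one whose level changes the difference between treatment and control. The Week 10 half of the outcome comes from a single open-label arm, so it cannot separate a predictive marker from a prognostic one. The study SAP takes the same position when it removes Week 6 and Week 10 efficacy outcomes for want of a comparator (section 2.2). Only the randomised Week 62 half can address the question in Protocol 3.3.4.

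That half is tied to maintained remission. Responders not yet in remission at Week 10 are randomised and count in the primary endpoint, but the definition closes the biomarker outcome to their Week 62 results. Precision is at stake in an analysis that already divides the sample by marker level, and so is the match between the biomarker result and the trial's main result. Study SAP 4.4.2.4 already treats Week 10 remitters as a small group and drops a stratification factor for that reason.

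**Working it through.** **Inputs**
- Enrolment (Protocol 6.1): "Approximately 350 patients will be enrolled in the open-label Induction Phase". Same section: 60% Week 10 response, about 105 per arm, a 25-point difference, placebo remission 30% to 45%, two-sided 5%.
- Phase II Week 10 clinical remission in TNF-naive patients (Protocol 1.3): 43.8% at 100 mg, 25% at 300 mg plus loading dose.

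**1. The plan's own figures**
- Randomised: 350 × 0.60 = 210, or 105 per arm.
- Power = Φ[(Δ√n − 1.96√(2p̄(1−p̄))) / √(p₁(1−p₁) + p₂(1−p₂))]. With p₁ = 0.30, p₂ = 0.55, n = 105: (2.562 − 1.370)/0.676 = 1.76, so 96.1%. Across placebo rates of 30% to 45% the result is 95.7% to 96.1%. The stated >90% is reproduced.

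**2. Share of randomised patients not in remission at Week 10**

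Every remitter is also a responder. Entry requires MCS of at least 6 and remission requires at most 2, a fall of at least 4 points and 67%, with rectal bleeding 0. So the remitter share of those randomised is s = remission rate / 0.60.

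| Week 10 rate | s | Remitters (210 × s) | Others | SE ratio √(1/s) |
|---|---|---|---|---|
| 43.8% | 0.730 | 153 | 57 (27%) | 1.17 |
| 25% | 0.417 | 88 | 122 (58%) | 1.55 |

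The SE ratio assumes the same outcome rates in remitters as in all randomised patients.

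**3. What each denominator does**
- *Remitters only.* The others are absent. As a yardstick, power for an overall 25-point difference falls from about 96% to 88.7% (about 77 per arm) or 66.2% (about 44 per arm).
- *All randomised, with Week 10 non-remitters as failures.* They cannot succeed in either arm. A 25-point difference among remitters shrinks to 0.730 × 25 = 18.3 points or 0.417 × 25 = 10.4 points. Protocol 3.3.4 also reports more Week 10 remission at higher alpha-E in Phase II. If that recurs, s is larger in the high group, and the between-arm difference would shrink less there even if the effect among remitters were equal.

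In neither case does the Week 62 result of a Week 10 non-remitter enter the arm comparison.

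**4. Illustration of the arm-by-marker contrast**

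Assume placebo 30%, an effect of 40 points in alpha-E high and 10 in low, and half the patients in each group. The four cells have rates 0.30, 0.70, 0.30 and 0.40, with N/4 patients each:

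SE = √[(0.21 + 0.21 + 0.21 + 0.24)/(N/4)], and power = Φ(0.30/SE − 1.96).
- N = 210: SE 0.129, power 64%.
- N = 153: SE 0.151, power 51%.
- N = 88: SE 0.199, power 32%.

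These effects are invented to show the direction. The documents state no biomarker power, cut-off or interaction test.

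**The case against.** Maintained remission is not a leftover. Version 7 keeps it in Table 1, lists Week 62 remission among Week 10 remitters as a secondary endpoint, and stratifies randomisation by Week 10 remission status. Crossing it with a biomarker is a legitimate exploratory choice, and Protocol 6.6 plans only descriptive biomarker summaries. This stands, and it is why the remitter view should be kept as a secondary one. It does not make that view the better main outcome for a predictive question.

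A reader might also infer more than the documents support:
- *That this is the only randomised look at alpha-E.* Not shown. The objective in Protocol 2.4 is wider, project SAP 4.4.3 allows added subgroups, and project SAP 4.6 refers to a Biomarker Analysis Plan that is not among the documents. It is only the sole listed outcome measure crossing baseline biomarkers with a randomised-phase efficacy endpoint.
- *That patients are certainly dropped.* No denominator is stated. The trial title also uses maintenance of remission loosely although the primary population is responders, so the authors may have meant plain Week 62 remission. If so, the text should say it.
- *That a promised alignment was missed.* The Version 7 rationale speaks of efficacy endpoints and does not cite 3.4.4.
- *That two thirds are lost.* This would divide the all-patient rate of 20.5%, which includes patients with inadequate response to TNF inhibitors, by a TNF-naive response rate. Like with like, the upper figure is 58%.
- *That every randomised patient has an observed Week 62 result.* Under study SAP 4.4, patients who discontinue are imputed as non-responders.

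**Conclusion.** The point holds as a minor improvement to an exploratory outcome. On the Table 1 definition, the Week 62 results of about 27% to 58% of randomised patients cannot contribute to the listed biomarker outcome, and standard errors are about 1.17 to 1.55 times larger than with all randomised responders. The lower figure uses the Phase II dose nearest to the trial dose. The upper one comes from the higher-dose regimen.

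The range rests on the planned 60% response and on TNF-naive subgroups of Phase II arms of about 40 patients, so it is imprecise. It also uses clinical remission as a stand-in for remission. The documents give no Week 10 rate on the stricter definition, which needs a rectal bleeding subscore of 0, so the affected share may be larger. The primary and key secondary tests are untouched.

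**What to change.** In Protocol 3.4.4, the synopsis and SAP Appendix 1:
- Define the randomised-phase biomarker outcome as MCS remission at Week 62 in all patients randomised as Week 10 clinical responders, tabulated by randomised arm and baseline biomarker level.
- Report the between-arm difference with its 95% CI at each biomarker level.
- Keep Week 10 remission by biomarker level as a descriptive single-arm summary, and Week 62 remission among Week 10 remitters as a secondary view with its denominator stated.
- Check that the Biomarker Analysis Plan uses the same definition, before treatment codes are opened for the Week 62 analysis.

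The cost is wording. The screening biopsy is already mandatory, and Week 62 status is already assessed or imputed for the primary endpoint, so no new procedure or data are needed.
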